explanation of these processes use the morphic / morphogenic field and -resonance concepts (cf. storage) of the biologist Rupert Sheldrake (Sheldrake, 2011) in combination with the function of mirror neurons (cf. way of accessing stored information by non-members of the system) (Lahore, 2009).

Regardless of whether we fully understand the exact mechanisms of action of a therapeutic modality and if its certain assumptions fit the contemporary paradigms of health sciences, we argue that collecting empirical data on an intervention's effectiveness and safety is a public health necessity, especially if it is so widely used as family constellation therapy is (and it certainly could provide further impetus to the study of the mechanisms of action and the potential reconsideration of the accuracy of our paradigms).

The very limited number of previous prospective, peer-reviewed studies into family constellation therapy's therapeutic effectiveness reported that the intervention was effective in reducing general, non-diagnosis-specific psychopathology and psychological distress (Hunger et al., 2015; Krüger & Schmidt-Michel, 2003; Weinhold et al., 2013) as well as improving quality of life and functioning in interpersonal relationships (Hunger et al., 2014; Hunger et al., 2015).

The aim of the present study was to collect and analyze further data from the real life setting on family constellation therapy's effectiveness in improving mental health and its tolerability 1) using a mid-term time frame (≥6 months) to evaluate client outcomes, 2) employing active monitoring (not just passive surveillance) of potential iatrogenic effects, and 3) providing information on the presence or absence of therapist effects.

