## Participants and procedure

Participants of the study will be recruited in Hungary from individuals in the general population who will express their intent to participate in a 2-day family constellation workshop on a fee-for-service basis (private setting) with one of the three professionals participating in the study. All three intervention providers will be highly trained in both general mental health care delivery (one therapist with a background in clinical psychology, while the other two will be trained in medicine) and family constellation therapy (10-20 years of experience). Participation in the study will be voluntary and will occur as a combination of online and paper-pencil data collection after participants give their informed, written consent. Neither the therapists nor the participants will receive financial compensation for their participation.

The assessment protocol will include a pre-intervention assessment, a follow-up approximately 4 weeks after the intervention (this time is estimated to be necessary for the single-occasion, 2-day workshop to have most of its effects; cf. the focus on changes in perceived quality of interpersonal relationships and related mental health symptoms), and finally, six months post-intervention. Significant efforts will be made (follow-up email and three attempted phone calls) to encourage participants to complete the questionnaires at both follow-up assessment points.

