#### Measures

Ad hoc items to assess sociodemographic characteristics and iatrogenic effects

To assess sociodemographic characteristics, questions will be administered to assess participants' sex, age, relationship/marital status, and educational attainment. A couple of freetext questions will also be asked to participants to explore potential iatrogenic effects (T2 & T3, Did you experience any negative change in relation to your mental or physical health during or since the family constellation workshop?). If respondents answer affirmatively to the second question, it will also be asked if they believe the changes are associated with their participation in family constellation therapy (yes, no, or unsure).

Brief Symptom Inventory (BSI)

The Hungarian version (Urbán et al. 2014) of the BSI (Derogatis & Spencer 1993) will be used to measure an individual's overall psychopathology level. This tool consists of 53 items covering nine symptom dimensions: somatization, obsessive-compulsive symptoms, interpersonal sensitivity, depression, anxiety, hostility, phobic anxiety, paranoid ideation, and psychoticism. Out of the three global measures of pathology and distress, the General Severity Index (GSI, mean of all items) will be used in the present study.

Experience in Personal Social Systems Questionnaire (EXIS.pers)

The Hungarian version of the EXIS.pers (Hunger et al. 2017) will be used to assess the subjective experiences of the individual in their personal social system (e.g., family, circle of friends).

Patient Health Questionnaire-15 (PHQ-15)

The Hungarian version of the PHQ-15 (Kroenke et al. 2002) will be used to evaluate the intrusiveness of somatic symptoms and a tendency toward somatization. The assessment tool contains 15 items, each addressing a frequently occurring mild, physical symptom such as back pain or trouble sleeping.

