#### **SCOFF**

The Hungarian version (Dukay-Szabó et al. 2016) of the SCOFF screening test (Morgan et al. 2000) will be used to measure non-disorder-specific risk level for eating disorders. At least two positive answers (score of 2) will indicate a high likelihood of an eating disorder (Dukay-Szabó et al. 2016).

Ad hoc items to assess addiction severity

In the absence of a concise and validated, broad-focus screening tool to assess the severity of both substance-related and behavioral addiction problems, a 4-item ad hoc tool will be created for the purposes of the present study. One question each will refer to the past-month frequency of substance use and excessive behaviors, while further two questions will explore the extent to which participants perceive that their substance use or excessive behaviors cause problems in their lives.

Meaning in Life Questionnaire (MLQ)

The Hungarian version (Martos & Konkolÿ Thege 2012) of the MLQ (Steger et al. 2006) will be used to assess both the presence of and search for meaning in a respondent's life as eudaimonic wellbeing indicators. While the former is an indicator of positive mental health, the latter is typically considered as an indicator of ill mental health and therefore, higher scores indicate less favorable mental status. The scale consists of 10 items (5 items measuring both subconstructs).

WHO Well-being Index (WBI-5)

The Hungarian (Susánszky et al. 2006), 5-item version of the WHO Well-being Index (Bech et al. 1996) will be used to measure participants' overall subjective well-being as a hedonic indicator of wellbeing.

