#### II. STATISTICAL ANALYSIS PLAN

All analyses will be carried out using SPSS for Windows. Baseline characteristics of study completers versus drop-outs will be compared using the Mann-Whitney U (age) and the chi-squared (categorical variables) test. Effect size will be expressed using effect size r (Mann-Whitney U test) and Cramer's V (Chi-squared test). Considering the likely non-normal distribution and occasionally ordinal nature (SCOFF) of the outcome variables, the effectiveness of the intervention will be investigated using Wilcoxon paired sample tests in the primary analyses. Separate comparisons will be made to explore potential changes from baseline to 4-week post-intervention as well as baseline to 6-month follow-up. Effect size r will be computed to express the magnitude of the changes.

Given that the normality assumption is relatively rarely examined and therefore parametric tests are used most often in effectiveness research, to facilitate inter-study comparability, repeated measures ANOVAs will be conducted as secondary analyses to investigate the main effect of time considering all three assessment points. For similar reasons, means and standard deviations (instead of medians and interquartile ranges) will be reported as descriptive data to allow easier comparisons across studies. A further set of ANOVAs will be run to investigate therapist effects. In these secondary analyses, effect size will be expressed by eta squared.

The Reliable Change Index (RCI) will be used to examine the clinical significance of changes on the individual level. Given the uncontrolled nature of the current study's design, a metric will be chosen that considers the tendency of regression to the mean, a threat to the validity of effectiveness studies without a control group. For this reason, the Edwards–Nunnally method will be used to examine the reliability of changes over time (Bauer et al. 2004).

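### The therapist-effects aim rests on a secondary set of ANOVAs over at least eight scores, with no deciding score and no correction within the set; read scale by scale at 5%, the chance of a false therapist effect is about 17-34%

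*Combined protocol and SAP*

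**What the plan says.** The protocol, under Background and aims, lists three aims. The third is "providing information on the presence or absence of therapist effects". Under Participants and procedure, clients attend a workshop "with one of the three professionals participating in the study", so there are three groups to compare.

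The SAP (second paragraph) gives this aim one sentence: "A further set of ANOVAs will be run to investigate therapist effects". The next sentence sets the status of the ANOVAs and how they are reported: "In these secondary analyses, effect size will be expressed by eta squared".

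The SAP does not state, for this set:
- which scores and time points are analysed;
- which term is tested (therapist main effect, therapist by time, or a comparison at one follow-up);
- the significance level;
- any multiplicity adjustment;
- what pattern of results would be reported as presence, or as absence, of a therapist effect.

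**The concern.** The aim is worded so that the report has to say whether therapist effects were found. The analysis behind it is a collection of tests, and different members of the collection can give opposite answers. Without a named deciding test, one significant scale out of eight could be reported as presence, or set aside as chance. Either choice could be made after the results are known.

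This family of tests is separate from the before-after effectiveness tests. Its null hypothesis is that the therapists do not differ, whether or not clients improve. Adjusting the Wilcoxon tests would leave it uncontrolled.

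At stake is the reliability of the answer to a declared aim in a study with only three providers.

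**Working it through.** The documents give no sample size, power, alpha or familywise error rate, so there is no planned figure to reproduce. The check computes what the set would do under stated assumptions.

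**Step 1: count the scores** (protocol, Measures, including the SCOFF subsection).

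| No. | Score | Basis |
|---|---|---|
| 1 | BSI | "the General Severity Index (GSI, mean of all items) will be used in the present study" |
| 2 | EXIS.pers | "will be used to assess the subjective experiences of the individual in their personal social system" (counted once; use of subscales is not stated) |
| 3 | PHQ-15 | "will be used to evaluate the intrusiveness of somatic symptoms and a tendency toward somatization" |
| 4 | SCOFF | "will be used to measure non-disorder-specific risk level for eating disorders" |
| 5 | Addiction items | four ad hoc items, counted as one score |
| 6, 7 | MLQ | presence and search, described as two subconstructs |
| 8 | WBI-5 | subjective well-being |

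Eight is a minimum. Analysing the four addiction items separately would make it 11.

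**Step 2: assumptions the documents do not supply.** Alpha 0.05 per test; one therapist test per score; any one significant score read as presence; correlation between scores from 0 to 0.8; total sample 60 or 120; clients independent.

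**Step 3: independent scores.** The chance of at least one false positive is 1 - (1 - alpha)^k.
- k = 8, alpha 0.05: 1 - 0.95^8 = 0.337
- k = 11, alpha 0.05: 1 - 0.95^11 = 0.431
- k = 8, alpha 0.01: 1 - 0.99^8 = 0.077

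**Step 4: correlated scores.** Simulation with three identical therapists, equal groups, eight equicorrelated normal scores, a one-way F test on each, and 20,000 replicates per setting:

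| Correlation | N = 60 | N = 120 |
|---|---|---|
| 0.2 | 31.7% | 31.8% |
| 0.3 | 30.7% | 30.2% |
| 0.4 | 28.1% | 28.7% |
| 0.5 | 25.6% | 25.5% |
| 0.6 | 23.2% | 23.1% |
| 0.7 | 20.3% | 19.6% |
| 0.8 | 16.7% | 16.6% |

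A 60/25/15% split of clients between therapists at correlation 0.5 also gives 25.6%. Sample size and imbalance therefore hardly matter; the number of scores and their correlation do.

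**Step 5: both follow-ups tested separately (16 tests).** If all are independent, 1 - 0.95^16 = 0.560. With a correlation of 0.5 between the two changes on the same score, simulation gives 50% at between-score correlation 0.3 and 43% at 0.5.

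**Step 6: effect of a correction.** Bonferroni at 0.05/8 = 0.00625 per score brings the simulated familywise error to 4.6-4.8% at correlation 0, 4.2% at 0.5 and 2.7-2.8% at 0.8.

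**Step 7: limit of the independence assumption.** Treatment is delivered in workshops of roughly 15 to 25 people (protocol, Intervention), and all clients in a workshop share a therapist. Take an assumed intraclass correlation of 0.05 and 20 analysed clients per workshop. The design effect is 1 + 19 × 0.05 = 1.95. With 2 numerator degrees of freedom, the large-sample error of a nominal 5% test is exp(ln(0.05)/1.95) = exp(-2.996/1.95) = 0.215, or about 22%. At an intraclass correlation of 0.01 the design effect is 1.19 and the error is exp(-2.996/1.19) = 0.081, about 8%. Fewer enrolled clients per workshop would reduce both.

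**The case against.** The strongest reply is that the SAP does rank this set. It is secondary, sits below the Wilcoxon tests and comes with an effect size. The aim speaks of providing information and the SAP of investigating, and neither says that one significant scale amounts to presence. Reporting each scale with its eta squared could meet the aim, since a therapist effect may be real on one scale and absent on another. Formal error control inside a secondary set of an uncontrolled study is partly a matter of judgement.

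Much of this stands, and it rules out several stronger readings that a reader might infer:

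- **That the set has no ranking at all.** It is unranked only internally.
- **That a one-in-four error rate follows from the plan.** It does not. It needs alpha 0.05, one test per score, a correlation near 0.5 and an any-scale rule, none of which is stated.
- **That 16 tests are planned.** The sentence follows a description of repeated-measures ANOVAs over all three assessments, so one therapist-by-time model per score is at least as natural. That gives about eight tests.
- **That a false positive would single out one provider, or invalidate pooling across therapists.** An omnibus F test does not identify a provider, no post-hoc comparisons are planned, and the SAP does not tie pooling to this test.

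It is also fair to say that the missing alpha, key outcome and multiplicity statement affect the whole SAP, and that one paragraph could cover both families.

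What the reply does not remove is that these ANOVAs are the only analysis for a declared aim. The secondary label orders the set against the Wilcoxon tests, not the scores within it. Eta squared has no threshold or interval attached that would turn it into a conclusion.

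**Conclusion.** The point holds in conditional form. Aim 3 depends on a secondary set of ANOVAs over at least eight scores, with no deciding score and no correction specified within the set. At 5% per test, with one test per score and any significant scale read as presence, the chance of a false therapist effect is about 17-34%, and near 25% at correlation 0.5. That is roughly three to seven times the nominal 5%. It is higher if each follow-up is tested separately, and lower with a stricter alpha (7.7% at 0.01 with eight independent scores).

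Two further inferences are not supported. A non-significant set would not show absence: no sample size is stated and no interval is planned. Nor would naming a single test guarantee 5%, because clients within a workshop may not be independent (Step 7).

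This should be settled before the therapist analyses are run. It does not by itself bear on the before-after effectiveness results.

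**What to change.** Replace the therapist-effects sentence in the second paragraph of the SAP with text along these lines:

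> Aim 3 will be decided by one contrast: the therapist-by-time comparison of change from baseline to 6 months on the BSI General Severity Index, at two-sided 5%. Therapist comparisons on all other scores, and on change to 4 weeks, are exploratory. They will be reported with Holm-adjusted p-values, and none alone will be taken as presence of a therapist effect. Eta squared will be given with a confidence interval for every comparison, and a non-significant result will not be read as absence. The nominal error rate assumes independent clients, which clustering within workshops may violate.

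Reasons for the choices:
- **Change from baseline.** Clients sign up with a given therapist and no random allocation is described. A raw 6-month comparison would mix in baseline differences between clienteles.
- **The named score.** The GSI is offered because the protocol uses it for overall psychopathology. The sponsor may name another, such as EXIS.pers, given the protocol's emphasis on interpersonal relationships. What matters is that one is named in advance.
- **Six months.** This matches the mid-term time frame in the first aim.

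The cost is a few sentences in the SAP, a column of adjusted p-values and an interval for each eta squared, with no new data. The downside is less power to declare a therapist effect confined to one non-key scale. Such a result would still be shown, labelled exploratory.

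### The therapist-effect aim is to be reported by eta squared alone, an upward-biased measure with no interval, which cannot support a statement of absence

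*Combined protocol and SAP*

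**What the plan says.** The protocol's Background and aims section lists three aims, the third being "providing information on the presence or absence of therapist effects". Under Participants and procedure, clients are people "who will express their intent to participate in a 2-day family constellation workshop on a fee-for-service basis", "with one of the three professionals participating in the study". There are therefore three groups, formed by the clients' own booking, with no quota or balancing described.

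The SAP gives this aim two sentences: "A further set of ANOVAs will be run to investigate therapist effects" and "In these secondary analyses, effect size will be expressed by eta squared". It does not say:
- what the dependent variable is (a change score, or a time-by-therapist term);
- whether eta squared will carry an interval;
- how presence or absence will be judged.

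For effectiveness the SAP does more. "Considering the likely non-normal distribution and occasionally ordinal nature (SCOFF) of the outcome variables", it says, "the effectiveness of the intervention will be investigated using Wilcoxon paired sample tests in the primary analyses". ANOVAs for the effect of time then sit beside those tests, with comparability to other studies given as the reason. No total N, number of clients per therapist, significance level or standard deviation is stated.

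**The concern.** Eta squared is the share of the sample's variation that lies between therapist means. Sample means differ by chance even when the therapists are equally effective, so the statistic is positive in practically every sample and overstates the population value. The overstatement is largest in small samples.

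That matters for an aim which has to be able to report absence. A reader shown a therapist eta squared of 0.02 or 0.03 without an interval cannot tell chance from a real difference. Nor can a non-significant F test fill the gap, because it does not show how large an effect remains compatible with the data. The plan as written could give a therapist effect that looks real when there is none, or a claim of absence that the data do not justify.

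**Working it through.** The documents give no figure to reproduce, so the size is worked out over assumed values of N.

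**Inputs.** Number of therapists k = 3 (Participants and procedure). Assumed: N = 60, 100, 200; significance level 5%; benchmark 0.01 for a small eta squared; normal errors with equal spread for steps 1 to 3.

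**1. Eta squared at zero effect.** It follows a Beta(1, (N-3)/2) distribution, so its mean is 2/(N-1) and P(exceeds x) = (1-x)^((N-3)/2).

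| N | Mean | P(exceeds 0.01) |
|---|---|---|
| 60 | 2/59 = 0.034 | 0.99^28.5 = 75% |
| 100 | 2/99 = 0.020 | 0.99^48.5 = 61% |
| 200 | 2/199 = 0.010 | 0.99^98.5 = 37% |

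If the model is instead time by therapist over three visits, partial eta squared under sphericity follows Beta(2, N-3). Its mean is again 2/(N-1), so the bias does not depend on which model is meant.

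**2. Omega squared at zero effect.** Omega squared = 2(F-1)/(2(F-1)+N), which averages about zero. It reaches 0.01 when F is at least 1 + N/198. That happens in 28%, 23% and 14% of samples at N = 60, 100 and 200: less often than for eta squared, but not rarely.

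**3. What an interval adds.** Suppose the observed F is exactly 1, so that omega squared is 0. The upper 95% limit for the population share of variance is L/(L+N), where L is the noncentrality at which a noncentral F with 2 and N-3 degrees of freedom falls at or below 1 with probability 0.025.
- N=60: L = 9.89, limit 9.89/69.89 = 0.14
- N=100: L = 9.86, limit 9.86/109.86 = 0.09
- N=200: L = 9.83, limit 9.83/209.83 = 0.05

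Even a point estimate of zero therefore leaves appreciable therapist effects open at these sizes. Only the interval shows this.

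**4. Error rate of the test.** Simulated with equal therapist means, assumed group sizes 20/30/60, nominal 5% and 40,000 data sets per cell. Skewed data are exponential and lognormal (log-scale SD 0.8). Each cell gives normal / exponential / lognormal.

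| SDs (groups of 20/30/60) | Classical F | Welch |
|---|---|---|
| 1/1/1 | 5.1 / 4.9 / 4.6% | 5.1 / 6.3 / 6.5% |
| 1.5/1.25/1 | 8.9 / 8.8 / 8.3% | 5.0 / 7.4 / 8.1% |
| 2/1.5/1 | 12.4 / 12.5 / 12.0% | 5.0 / 8.0 / 9.4% |
| 1/1.25/1.5 | 2.7 / 2.9 / 3.2% | 5.0 / 5.5 / 5.3% |

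Skewness alone (first row) leaves the classical test near 5%. The drift, from about 3% to 12%, needs unequal sizes together with unequal spread. Welch corrects it for normal data but runs at about 5% to 9% with skewed data.

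**The case against.** **Secondary status and comparability.** These ANOVAs are labelled secondary, and the SAP defends parametric methods in the same paragraph: "to facilitate inter-study comparability, repeated measures ANOVAs will be conducted as secondary analyses". Both points lower the weight. The stated reason is attached to the time-effect ANOVAs rather than expressly to the therapist ones, and comparability is kept if eta squared is reported beside the corrected measure.

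**The F test would settle presence, not eta squared.** At N=60, p<0.05 needs 1 - 0.05^(1/28.5), that is, an eta squared of about 0.10, so a chance value of 0.03 would not be called significant. This stands for presence. It does not help with absence.

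**Omega squared also strays above 0.01 by chance.** True (step 2), and the reason why the interval matters more than the choice of point estimate.

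**A reader might infer that the SAP's own expectation of non-normal and ordinal outcomes makes ANOVA invalid here, so that a robust or rank test must replace it.** The figures do not support that. Non-normality alone does not move the error rate, the documents give neither group sizes nor spreads, and the SAP writes only of ANOVAs without excluding a Welch version. Welch is slightly worse than the classical test for skewed data with equal spread. Kruskal-Wallis is no clean substitute either: in runs with skewed data, unequal spread and equal means it rejected in about 7% to 59%, because it also responds to shape.

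**Clustering by workshop may be a larger threat.** Clients attend in groups of about 15 to 25. With an assumed 20 per workshop, two or three workshops per therapist and no therapist effect, F rejects about 11% of the time at a workshop intraclass correlation of 0.02, and 22% at 0.05. This is a separate issue. The change proposed here does not address it, and an interval that ignores clustering would be too narrow.

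**Conclusion.** The point holds for the effect size. The third aim rests on a statistic that averages 2/(N-1) when there is nothing to find and is planned without an interval, so the plan as written cannot support a statement of absence. The figures are exact for three groups with normal errors and equal spread. N is assumed throughout.

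Two stronger readings do not hold. That a zero effect will generally show as small depends on a 0.01 benchmark that the SAP does not adopt, and on N: the mean is at or above 0.01 only up to N = 201 (2/200 = 0.010), and the chance of exceeding it is already down to 37% at N=200. That the planned test has the wrong error rate is a conditional risk, resting on unequal sizes and unequal spreads that the documents neither give nor rule out. It justifies a sensitivity analysis, not a change of main test. The improvement is worth making because it is nearly free, but it concerns a secondary analysis.

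**What to change.** In the SAP paragraph on secondary analyses:

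1. Name the outcome for the therapist comparison, for example change from baseline at 4 weeks and at 6 months. Welch's test, being one-way, needs this choice as well.
2. Report omega squared, or another bias-corrected measure, with a 95% confidence interval for the therapist effect, and keep eta squared beside it for comparison with other studies.
3. State that any conclusion of absence will rest on the upper limit of that interval, and say in advance what limit would count as negligible. Otherwise report that the data do not settle the question.
4. Add Welch's ANOVA as a sensitivity analysis, with the number of clients and the SD per therapist shown so that readers can judge whether the classical test is at risk.

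The cost is a few sentences and a little more output; omega squared follows directly from F and N. The point estimates will be smaller and sometimes slightly negative, which should be read as zero. At modest N the interval may be too wide to claim absence. The usual noncentral-F interval shares the ANOVA's assumptions, so it needs the same caution with skewed outcomes. Clustering by workshop has to be handled separately.

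### The Edwards–Nunnally result is labelled clinical significance with no clinical criterion and no expected no-change rate; under the usual formula (assumed, none is printed) about 12.5–15% of unchanged clients would be flagged

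*Combined protocol and SAP*

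**What the plan says.** The third paragraph of the SAP (section II) introduces the individual-level analysis: "The Reliable Change Index (RCI) will be used to examine the clinical significance of changes on the individual level". It notes that the study is uncontrolled and that therefore "a metric will be chosen that considers the tendency of regression to the mean". It then names the rule: "the Edwards–Nunnally method will be used to examine the reliability of changes over time".

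The paragraph cites a paper comparing clinical significance methods. It prints no formula, multiplier or confidence level, and no source for the reliability r, the mean M or the SD. It does not name the outcomes that will receive the index. No cut-off or minimal important change goes with it. The one clinical threshold in the documents, a SCOFF score of at least 2 (protocol, Measures), is not tied to this analysis. None of these gaps comes from redaction.

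**The concern.** Two things are at stake.

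**The label.** A change larger than measurement error is a reliable change. Whether it matters to the client is a separate question that needs a separate criterion. The paragraph uses both descriptions for one analysis, and only the reliability description fits what is planned.

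**The benchmark.** Any such rule flags some clients who have not changed. A control arm would show how many. Here there is none, and the plan states no expected rate. A reader told that a certain percentage changed significantly cannot tell how much of it is chance. The named rule makes this more pressing, because in its usual form it flags well over the nominal 5%. The protocol also lists tolerability among its aims, so chance flags of deterioration matter as well as chance flags of improvement.

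**Working it through.** The documents give no flag rate, reliability or multiplier, so there is no planned figure to reproduce.

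**Inputs, all assumed.** The rule is the usual Edwards–Nunnally form: flag a client whose follow-up score lies outside M + r(X − M) ± k·SD·√(1 − r), where X is the baseline score. Reliability r is 0.70 to 0.95, and k is 2 or 1.96. There is no true change, variances are equal, the group mean does not drift, and the true correlation s between the two occasions (the stability) equals r unless stated.

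**Step 1: band against spread.** The half-width is k standard errors of measurement, k·SD·√(1 − r). An unchanged client's follow-up score varies around the predicted value with standard deviation SD·√(1 − r²) = SD·√(1 − r)·√(1 + r). The band is therefore too narrow for its nominal level by the factor √(1 + r).

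**Step 2: flag rate.** The rate per direction is 1 − Φ(k/√(1 + r)), and the total is twice that. Example, r = 0.70 and k = 2: 2/√1.70 = 1.534, giving 6.25% per direction and 12.5% in total.

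| r | total, k = 2 | per direction, k = 2 | total, k = 1.96 |
|---|---|---|---|
| 0.70 | 12.5% | 6.3% | 13.3% |
| 0.80 | 13.6% | 6.8% | 14.4% |
| 0.90 | 14.7% | 7.3% | 15.5% |
| 0.95 | 15.2% | 7.6% | 16.0% |

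The nominal totals are 2(1 − Φ(2)) = 4.55% and 5.0%. Simulation with 2,000,000 clients per value of r agrees to within 0.1 point.

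**Step 3: entered r differs from stability.** The spread becomes SD·√(1 + r² − 2rs), and the total is 2[1 − Φ(k√(1 − r)/√(1 + r² − 2rs))]. With k = 2 and s = 0.80:

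- r = 0.70 entered: 1.095/√0.37 = 1.095/0.608 = 1.801, total 7.2%.
- r = 0.90 entered: 0.632/√0.37 = 0.632/0.608 = 1.040, total 29.8%.

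**Step 4: non-normal scores.** The SAP expects this: "Considering the likely non-normal distribution and occasionally ordinal nature (SCOFF) of the outcome variables". Simulated skewed true scores with constant error (k = 2) gave 6.1% improved and 6.4% deteriorated at r = 0.70, and 7.3% and 7.4% at r = 0.90. Skewness alone hardly moves the split. A floor does. Floored, discrete symptom scores (beta-binomial, 15–40 points, skewness 0.7–1.4, r 0.71–0.85, all assumed) gave 4.5–5.4% improved and 7.5–8.3% deteriorated.

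**Step 5: regression to the mean.** The term r(X − M) pulls each client towards M and so allows for individual measurement error. Suppose M is the sample's own mean and the whole group starts d SDs above its long-run level. The expected follow-up then falls (1 − s)·d SDs below the prediction (taking r = s), and nothing in the rule removes that shift.

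**Step 6: the wider band.** With ±1.96·SD·√(1 − r²) and s = r, the total is 5% for symmetric scores. It costs sensitivity. For a true 1 SD gain at r = 0.80 the residual SD is √(1 − 0.64) = 0.6. The usual band detects Φ((1 − 0.894)/0.6) = 57%, and the wider band Φ((1 − 1.176)/0.6) = 38%.

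**The case against.** The strongest reply is that the percentages rest on a formula the SAP does not print. It names a method and cites a comparison paper. The multiplier, M and r are open, and a √(1 − r²) band at 1.96 would give 5%. That is correct, and it limits the numerical part to a conditional statement. It does not touch the label, the missing criterion or the missing benchmark, which can be read directly from the text. The spread of possible rates is itself a reason to fix the inputs.

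The index is also supplementary. The paragraph does use the word reliability, and the cited paper's title speaks of clinical significance methods. This makes the labelling point modest but does not remove it, since results may be reported under the label.

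Some stronger readings are tempting, and the documents do not support them:

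- **That the rate will be near 30%.** This needs an internal consistency well above the retest stability. The SAP does not say which kind of r will be entered, and an r below stability lowers the rate.
- **That chance flags will mostly count as deterioration.** The SAP expects non-normal scores, not floored ones. Recruiting "individuals in the general population who will express their intent to participate in a 2-day family constellation workshop" makes a floor on symptom scales plausible but does not establish it. Where it occurs, the tilt works against the intervention.
- **That the SAP claims to remove regression of the whole group.** It says only that the metric takes regression to the mean into account, and it does not set M.
- **That the index is planned for every scale at both intervals, or was chosen for comparability.** The sentence "Separate comparisons will be made to explore potential changes from baseline to 4-week post-intervention as well as baseline to 6-month follow-up" concerns the Wilcoxon tests, and "to facilitate inter-study comparability, repeated measures ANOVAs will be conducted as secondary analyses" concerns the ANOVAs. The stated reason for Edwards–Nunnally is regression to the mean.
- **That one unchanged client in seven or eight would be called improved.** That fraction counts both directions.

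**Conclusion.** The point holds as an inexpensive improvement to a supplementary analysis. From the text alone, one analysis carries two descriptions, the stronger one has no clinical criterion behind it, and nothing in the plan or design shows what rate to expect without change.

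Conditional on the usual formula, stability equal to r and no group drift, the total flag rate among unchanged clients is about 2.5 to 3.5 times nominal: 12.5/4.55 = 2.7 to 15.2/4.55 = 3.3 at k = 2, and 13.3/5.0 = 2.7 to 16.0/5.0 = 3.2 at k = 1.96. The even split between directions holds for roughly symmetric scores and nearly so for skewed ones. On floored symptom scales, if there are any, it would be about 5% improved against 8% deteriorated.

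The Wilcoxon comparisons, which are the primary analyses, do not use this rule and are unaffected.

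**What to change.** 1. **Label.** Call the result reliable change, not clinical significance. State that it does not remove group-level regression or natural recovery.
2. **Specification and reporting.** Fix the formula, k, M and the source of r, and name the outcomes and intervals that receive the index. For each, report the percentage reliably improved and the percentage reliably deteriorated, with exact 95% confidence intervals, beside the expected no-change rate per direction. For roughly symmetric scores under the usual band that rate is 1 − Φ(k/√(1 + r)). If r is not a retest correlation for the interval, also give the rate at lower stabilities, using the formula in step 3. For clearly floored scales, simulate it: draw correlated normal pairs, map both members by rank onto the observed baseline scores, tune the correlation to r, and apply the rule. In five test settings this came within 0.3 percentage points of the true rate.
3. **Sensitivity analysis.** Add the ±1.96·SD·√(1 − r²) band and keep the named method as the main rule. The wider band is not a replacement, because it loses detection (38% against 57% for a true 1 SD gain at r = 0.80). Nor does it cure a wrong r: with r = 0.90 entered and stability 0.70 it still flags 24.9%.

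The cost is SAP wording and a little extra analysis, with no added clients or visits. The simulation may have to be run outside SPSS, to which the SAP now commits all analyses, so that sentence would need an exception. The reliable-change percentage will read less favourably with its benchmark beside it.
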